6. STUDY ENDPOINTS

6.1. Safety Endpoints

The safety endpoints include:

- The incidence of overall AEs, serious AEs, and AEs or SAEs leading to discontinuation
- Clinical laboratory evaluations (serum chemistry, hematology, urinalysis)
- Clinical evaluations (vital signs including orthostatic effects, and 12-lead ECGs)
- Frequency and severity of suicidal ideation and suicidal behavior using the C-SSRS
- Change and percent change in body weight and BMI
- Change in fasting lipid panel (triglycerides, total cholesterol, high-density lipoprotein [HDL] cholesterol, and low-density lipoprotein [LDL] cholesterol)
- Change in hemoglobin A1c levels
- Change in fasting glucose levels
- Change in the symptoms of withdrawal from dasotraline from Week 52/end of treatment (EOT) as measured by
 - CSSA total score at Weeks 53, 54, and 55
 - DESS total score at Weeks 53, 54, and 55
 - HAM-A total score at Weeks 53, 54, and 55
 - MADRS total score at Weeks 53, 54, and 55

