11.5. Study Visits and Assessments

11.5.1. Open-label Baseline: Visit 1E (Day -1)

Subjects will be evaluated at the Open-label Baseline Visit to determine their eligibility to enroll in the study. The following study-related procedures will be performed at Open-label Baseline:

Confidential and Proprietary

- Obtain informed consent
- Review inclusion/exclusion criteria
- Demographics
- Administer EDE-Q modified (Subjects from Study SEP360-221 only)
- Dispense study drug (First dose taken the following day on Day 1)

Results for the following study-related procedures will be carried over from the core study Week 12 visit, and do not need to be performed for the Open-label Baseline visit:

- Physical and neurological examinations
- Vital signs, weight, and BMI
- ECG
- Scales: BE-CGI-S, SDS, SF-12 (Subjects from Study SEP360-221 only), C-SSRS, HAM-A, MADRS, and EDE-Q modified (Subjects from Study SEP360-321 only)
- Clinical laboratories (serum chemistry, lipid panel, hemoglobin A1c, hematology, urinalysis), UDS, and urine pregnancy test for females of child bearing potential
- Breath alcohol test

AEs and concomitant medications ongoing at the Week 12 visit in the core study will be carried over. Other data such as height will be carried over from other visits in the core study.

Further information on data carried over from the core study will be addressed in the DMP.

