15.3.3.1. Adverse Events

All AEs will be coded using Medical Dictionary for Regulatory Activities (MedDRA) version 18.0 or higher.

Treatment-emergent adverse events (TEAEs) are those reported adverse events with onset data on or after the first day of the open-label treatment period through 7 days after study drug discontinuation (14 days for serious adverse events and deaths). The start of the open-label treatment period is defined as Day 1 for subjects previously randomized to placebo group and the OL Baseline visit date for subjects previously randomized to dasotraline groups.

A discontinuation-emergent adverse event (DEAE) is defined as an AE which has an onset after the last dose date of study drug through the Week 55 visit (ie, the last study visit in the withdrawal period).

Table summaries of AEs will be limited to TEAEs and DEAEs. All AE data will be displayed in data listings. For the sake of simplicity, hereafter TEAE is referred to as AE in this section.

The overall incidence (ie, number and percent of subjects with one or more AE in each category) of AEs, serious AEs, deaths, AEs leading to discontinuation, study drug-related AEs, study drug-related AEs leading to discontinuation, serious AEs leading to discontinuation, and serious study drug-related AEs, and serious study drug-related AEs leading to discontinuation will be summarized by analysis group.

The AEs also will be summarized by system organ class (SOC) and preferred term (PT) by presenting the number and percentage of subjects with each AE category. The incidence of AEs (by preferred term, grouped by SOC, and presented by analysis group) also will be summarized by severity, by the relationship to study medication, by the action taken regarding the study medication, as well as by the outcome.

The incidence of AEs of special interest, including but not limited to neuropsychiatric-related and cardiovascular-related AEs, will be summarized by analysis group. For time to the earliest onset of insomnia, Kaplan-Meier curves will be plotted by analysis group.

The overall incidence of DEAEs and serious DEAEs will be summarized by analysis group. The DEAEs also will be summarized by SOC and PT by presenting the number and percentage of subjects with each AE category.

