6.1.11.3. Incomplete/Missing Dates

6.1.11.3.1. Start/End Dates for Adverse Event

Treatment-emergent adverse events (TEAEs) are those reported adverse events with an onset date on or after the first day of the open-label treatment period (See [Section 6.1.1.1](#) for definition of the OL treatment period), through 7 days after study drug discontinuation (14 days for serious adverse events and deaths).

A conservative approach will be used to handle the missing dates for AE onset date and end date to identify the treatment-emergent AE (ie, if the available incomplete date cannot determine treatment emergent status, the AE will be considered as a treatment-emergent AE). No imputation is to be done to calculate AE duration.

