7.4.2. Adverse Events

All AEs are coded using Medical Dictionary for Regulatory Activities (MedDRA) version 19.0 or higher.

Treatment-Emergent Adverse Event (TEAE)

Treatment-emergent adverse events (TEAEs) are those reported adverse events with onset data on or after the first day of the open-label treatment period through 7 days after study drug discontinuation (14 days for serious adverse events and deaths). The start of the open-label treatment period is defined as Day 1 for subjects previously randomized to placebo group and the OL Baseline visit date for subjects previously randomized to dasotraline groups.

AEs with a start date prior to the first day of the OL treatment period which are reported to have an increase in intensity, or which are reported to have a attribution in relationship to study medication (ie, attribution to possible related, probably related, related) after the first day of the OL treatment period are considered as TEAEs.

Discontinuation-emergent adverse events (DEAEs) are defined as AEs which have an onset after the last dose date of study drug through the Week 55 visit (ie, the last study visit in the withdrawal period).

Table summary of AEs will be limited to TEAEs and DEAEs. All AE data will be displayed in data listings. For the sake of simplicity, hereafter TEAE is referred to as AE.

The overall incidence (ie, number and percent of subjects with one or more AE in each category) of AEs, serious AEs, deaths, AEs leading to discontinuation, study drug-related AEs, study drug-related AEs leading to discontinuation, serious AEs leading to discontinuation, and serious

study drug-related AEs, and serious study drug-related AEs leading to discontinuation will be summarized by analysis group.

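### An AE carried over from the core study that stops dasotraline or turns serious, without worsening or a related attribution in the extension, is missing from the tabulated incidence of SAEs and AE discontinuations, and the TEAE definition is inconsistent

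*SAP*

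**What the plan says.** The primary objective (Protocol 5.1, SAP 2.1) names AEs, discontinuations due to AEs, and SAEs. The matching endpoint in Protocol 6.1 is "The incidence of overall AEs, serious AEs, and AEs or SAEs leading to discontinuation".

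Protocol 11.5.1 brings core-study events into the extension: "AEs and concomitant medications ongoing at the Week 12 visit in the core study will be carried over". Their onset precedes the open-label (OL) period.

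SAP 7.4.2 restricts the tables ("Table summary of AEs will be limited to TEAEs and DEAEs"), and Protocol 15.3.3.1 does the same ("Table summaries of AEs will be limited to TEAEs and DEAEs"). Both then use AE as shorthand for TEAE. The planned incidences of serious AEs, AEs leading to discontinuation, and serious AEs leading to discontinuation are therefore TEAE incidences.

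The TEAE definition is given three times:

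- SAP 7.4.2 starts from onset ("adverse events with onset data on or after the first day of the open-label treatment period"). It then adds two ways in for earlier events. One is worsening: "AEs with a start date prior to the first day of the OL treatment period which are reported to have an increase in intensity". The other is an attribution to study medication of at least possible. The sentence closes with "after the first day of the OL treatment period are considered as TEAEs".
- SAP 6.1.11.3.1 gives onset only: "adverse events with an onset date on or after the first day of the open-label treatment period".
- Protocol 15.3.3.1 also gives onset only, with no route for earlier events.

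SAP section 4 states that nothing has changed from the protocol's planned analyses.

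**The concern.** Whether a subject stopped drug because of an AE, or had a serious AE, during the extension does not depend on when the event began. The tables make it depend on that, softened only by the worsening and attribution routes. Neither route mentions drug withdrawal or seriousness.

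Seriousness is not covered by the worsening route. Protocol 12.1.2 separates serious from severe: the first rests on outcome or action criteria, the second on intensity. An event can become serious with no recorded rise in intensity. Likewise, a subject can stop because an event has persisted unchanged.

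The stake is the tabulated incidence for two measures in the primary objective of a long-term safety study. An omitted event can only lower them. The inconsistent definitions add a second problem: a programmer cannot tell from the documents which rule governs, and the choice changes the counts.

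**Working it through.** No arithmetic decides this point. The check applies each written definition to a carried-over AE (onset before the OL period) that, during the OL period, leads to drug withdrawal or first becomes serious.

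| Carried-over AE that stops drug or turns serious | SAP 7.4.2 | Protocol 15.3.3.1 and SAP 6.1.11.3.1 |
|---|---|---|
| (a) Intensity increases in the OL period | Counted | Not counted |
| (b) Attributed to study drug after the first OL day | Counted | Not counted |
| (c) Intensity unchanged, no related attribution in the OL period (judged not related) | Not counted | Not counted |
| (d) Intensity unchanged, judged related only in the core study | Unclear | Not counted |

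**Could another rule rescue case (c)?**

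1. The DEAE definition requires onset after the last dose, so a carried-over AE cannot be a DEAE.
2. The conservative rule in SAP 6.1.11.3.1 concerns incomplete dates. It does not help an event with a known core-study onset.
3. The AESI, by-exposure and subgroup tables in SAP 7.4.2 are also built from TEAEs, so they inherit the gap.
4. The full AE listing includes events whatever their treatment-emergent status, but a listing gives no incidence.
5. The disposition summary (SAP 7.1.2) counts reasons for discontinuation with no TEAE filter, and adverse event is one of the recorded reasons (Protocol 13.1). It captures the stop, but not the preferred term, relatedness or seriousness. It gives nothing for an SAE in a subject who stays on drug.

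**Why case (d) is unclear.** The attribution route asks for an attribution reported after the first OL day. It does not say that the attribution must be new. If the investigator reassesses the event as related in the OL period, it is counted. If the only assessment on record dates from the core study, the sentence does not settle it.

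**Size.** The documents give no number of subjects in (c) or (d). With the planned enrollment of about 500, each subject who is omitted, and has no other qualifying TEAE in the same category, lowers the All-Das incidence by 1/500 = 0.2 percentage points.

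**The case against.** The strongest reply is that SAP 7.4.2 is not onset-only. Its worsening and attribution routes bring in many of the events at issue, and what remains is narrow. That stands. A reader might infer that every carried-over AE is lost, but that is true only of the other two definitions.

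A reader might also infer that core-onset insomnia, already judged related and then causing a stop at Week 8, is certainly missing. The text does not support that. This is case (d), and on a plain reading an event still judged related when the subject stops may well be counted. SAP 7.4.2 also plans a daily insomnia prevalence plot whose definition carries no onset condition.

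Nor are the events hidden: they are listed, and a stop for an AE is counted in disposition, where a mismatch with the AE table would be visible. That also stands, but the plan includes no reconciliation of the two counts, and disposition does not cover SAEs.

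Some carried-over conditions that become serious will also have worsened, or will be recorded as a study AE in their own right, since Protocol 12.1.1 treats exacerbation of a pre-existing condition as an AE. Recording rules for carried-over events are left to the Data Management Plan, which is not available here. It could narrow the gap in practice, but the written TEAE definition would still be silent.

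Finally, a reader might infer that Das-Das is made to look better tolerated than Pbo-Das by a quantifiable amount. Ongoing AEs that began on dasotraline can arise only in Das-Das, but the rule applies to both groups, no comparison is planned, and the core-study allocation ratios are not given. The discontinuation rates of 11.2% and 29.7% in Protocol 4.3 come from an adult ADHD study and say nothing about carried-over events.

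**Conclusion.** The point holds in a limited form. Under SAP 7.4.2, a carried-over AE of unchanged intensity, with no related attribution in the OL period, that leads to drug withdrawal or becomes serious is left out of the tabulated incidence of AEs leading to discontinuation and of SAEs. One judged related only in the core study has unclear status. Under the onset-only definitions, even worsened carried-over AEs are excluded, and SAP section 4 does not acknowledge the difference.

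The direction is certain: the tables can only undercount. The size is unknown, and any percentage would rest wholly on assumed rates. The conclusion assumes that a carried-over AE keeps its core-study onset date and is not re-entered as a new event when it becomes serious or stops treatment. The case for acting rests on the place of these measures in the primary objective and on the low cost of correction, not on a demonstrated large bias.

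**What to change.** 1. Use one TEAE definition in Protocol 15.3.3.1, SAP 6.1.11.3.1 and SAP 7.4.2. If the wider SAP 7.4.2 rule is kept, record it in SAP section 4 as a change from the protocol, and say whether a related attribution made only in the core study qualifies.
2. Tabulate SAEs and AEs leading to discontinuation for all AEs whose drug withdrawal or first seriousness falls in the TEAE window, whatever the onset date, with a separate row for those begun in the core study. Alternatively, add this as a further route in the TEAE definition.
3. Reconcile the number of subjects with an AE leading to discontinuation against the disposition reason of adverse event, and explain any difference.

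The cost is a short SAP edit and a small derivation change. Protocol 12.3 already has seriousness and action taken recorded for each AE. The documents do not say whether the date of becoming serious is a separate field; if it is not, it would have to come from the SAE report. The stated rates may rise slightly. The separate row keeps the count of events begun in the extension visible, which helps if the interim analysis, run under its own SAP, used a narrower rule.

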12.3. Collection and Recording of Adverse Events

All AEs must be collected and recorded in the subject's study records/source documents, in accordance with the Investigator's normal clinical practice, and on the CRF. All AEs will be followed up until resolution, stabilization of the condition, the event is otherwise explained, or the subject is lost to follow-up.

Each AE is to be evaluated for duration, severity, frequency, seriousness, action taken with the study treatment, outcome, and causal relationship to the study treatment. Definitions for severity, frequency, action taken with the study treatment, outcome, and causal relationship to the study treatment are presented below.

The severity of AE:

- **Mild** Ordinarily transient symptoms that do not influence performance of subject's daily activities. Other treatment is not ordinarily indicated.
- **Moderate** Marked symptoms sufficient to make the subject uncomfortable. Moderate influence on performance of subject's daily activities. Other treatment may be necessary.
- Severe Symptoms cause considerable discomfort. Substantial influence on subject's daily activities. May be unable to continue the study, and other treatment may be necessary.

The frequency of AE:

- **Once** an isolated episode
- Intermittent occurs on 2 or more separate occasions
- **Continuous** does not abate from date of onset to date of resolution

The action taken with the study treatment:

- **Drug Interrupted** Study medication stopped temporarily
- Drug Withdrawn Study medication stopped permanently
- Dose Reduced
- Dose Increased
- Dose not Changed
- Not Applicable

The outcome of the AE:

- Recovered/Resolved
- Recovering/Resolving
- Not Recovered/Not Resolved
- Recovered/Resolved with Sequelae
- Fatal

Confidential and Proprietary

• Unknown

The causal relationship of the AE to the study treatment:

- Not related
 - **Not related** Improbable temporal relationship and is plausibly related to other drugs or underlying disease.
 - **Unlikely** occurred within a reasonable time frame after administration/discontinuation of the study medication, but there is a likely association of an intercurrent/underlying medical condition or other drugs.
- Related.
 - **Possible** occurred in a reasonable time after study-medication administration, but could be related to concurrent drugs or underlying disease.

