The AEs also will be summarized by system organ class (SOC) and preferred term (PT) by presenting the number and percentage of subjects with each AE category. The incidence of AEs (by preferred term, grouped by SOC, and presented by analysis group) will also be summarized by severity, by the relationship to study medication, by the action taken regarding the study medication, as well as by the outcome. If a subject has the same AE on multiple occasions, the highest severity (severe, moderate, mild) recorded for the event and the highest drug relationship (unrelated, unlikely to be related, possibly related, probably related, and definitely related) will be presented, respectively. The relationship to study medication will be presented by 2 categories: related (which includes possibly related, probably related, and related, as determined by investigators), and not related (which includes unrelated and unlikely to be related, as determined by investigators). Furthermore, for AE summary by SOC and PT or by PT only, the following combined preferred terms will be summarized as well:

- Insomnia: Insomnia, Initial insomnia, Middle insomnia, Terminal insomnia
- Hallucination: Hallucination; Hallucination, auditory; Hallucination, gustatory; Hallucination, olfactory; Hallucination, synaesthetic; Hallucination, tactile; Hallucination, visual; Hallucinations, mixed; Hypnagogic hallucination; Hypnopompic hallucination; Somatic hallucination.

A Kaplan-Meier plot of the time to the first onset of treatment emergent insomnia (combined term) during the extension study will be presented by analysis group. Time to the first onset (in days) is defined as the earliest onset date of insomnia – start date of OL treatment period + 1. Subjects who do not experience any insomnia on or before the last dose date will be censored on the day of last dose.

Prevalence rate of insomnia (combined term) at a study day in the open-label treatment period is defined as number of subjects experiencing insomnia on the day divided by number of subjects remaining on open-label study treatment period at that time point. It is notable that subjects may experience multiple insomnia episodes during the study. Prevalence rate over time will be summarized and presented graphically by analysis group.

AE maximum relationship

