Each AE will be classified as ‘related’, ‘not related’, and ‘not specified’. TEAEs with a missing AE relationship will be classified as ‘not specified’. AE summary by the relationship to the study medication will be based on the highest relationship within an SOC and PT. Response values will be ranked in order from minimum to maximum as ‘not specified’ < ‘not related’ < ‘related’.

AE maximum severity

322

AEs with a missing severity will be classified as ‘not specified’. AE summary by the severity will be based on the maximum severity within an SOC and PT. Response severity values will be ranked in order from minimum to maximum as ‘not specified’ < ‘mild’ < ‘moderate’ < ‘severe’.

AE maximum action taken

AEs with a missing action taken will be classified as ‘unknown’. AE summary by the action taken will be based on the maximum action taken within an SOC and PT. Response action values will be ranked in order from minimum to maximum as ‘not applicable’ < ‘unknown’ < ‘dose increased’ < ‘unchanged’ < ‘dose reduced’ < ‘drug interrupted’ < ‘drug withdrawn’.

AE maximum outcome

AEs with a missing outcome will be classified as ‘unknown’. AE summary by the outcome will be based on the maximum outcome within an SOC and PT. Response outcome values will be ranked in order from minimum to maximum as ‘unknown’ < ‘recovered/resolved’ < ‘recovered/resolved with sequelae’ < ‘recovering/resolving’ < ‘not recovered/not resolved’ < ‘fatal’.

AEs of Special Interest (AESI)

A list of preferred terms that are to be combined for assessment of each of pre-specified adverse events category as below are provided in [Attachment 9.3](#).

- cardiovascular-related AEs
 - Cardiac arrhythmias
 - Vital signs-related
- metabolic-related AEs
 - Weight-related
 - Metabolic-Related (excluding weight)
- Neuropsychiatric-related AEs,
 - Neuropsychiatric AEs
 - Psychosis or Mania
 - Psychosis
 - Mania
- Combined insomnia
- Suicide and self-injury related AEs
- Spontaneous abortion /miscarriage (for female subjects only).
- Drug abuse and dependence (for AEs onset on/prior to the last study dose)
- Potential drug abuse (for AEs onset on/prior to the last study dose)
- Drug withdrawal related AEs (for AEs onset after the last study dose)

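### For subjects with repeat events, the AE 'maximum' rules let a benign known outcome, relationship or severity mask a missing one, and an event with missing causality has no stated place in the two-category relationship display

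*SAP*

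**What the plan says.** SAP 7.4.2 gives missing values their own class. For outcome, "AEs with a missing outcome will be classified as ‘unknown"; for relationship, "TEAEs with a missing AE relationship will be classified as ‘not specified". Missing severity is also 'not specified'.

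It then reduces each subject to one value: "AE summary by the outcome will be based on the maximum outcome within an SOC and PT", with parallel rules for relationship and severity. The rankings place the missing class at the bottom. For outcome, "Response outcome values will be ranked in order from minimum to maximum as ‘unknown’ < ‘recovered/resolved", followed in rising order by recovered with sequelae, recovering, not recovered and fatal. For relationship, "Response values will be ranked in order from minimum to maximum as ‘not specified’ < ‘not related’ < ‘related". For severity the order is 'not specified', mild, moderate, severe.

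Earlier in the same section, on the SOC and PT tables, the SAP says "The relationship to study medication will be presented by 2 categories": related (possibly related or stronger) and not related (unrelated or unlikely), both as judged by the investigator. The overall incidence table has rows for drug-related AEs, serious drug-related AEs, and each of these leading to discontinuation.

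Protocol 12.3 lists 'Unknown' and 'Not Recovered/Not Resolved' as separate outcome codes. On follow-up it says "All AEs will be followed up until resolution, stabilization of the condition, the event is otherwise explained, or the subject is lost to follow-up".

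**The concern.** A 'maximum' rule is meant to show the worst value a subject had. With the missing class at the bottom, a benign known value on one record displaces a missing value on another, and the table no longer shows that anything was missing.

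Repeat records are expected. SAP 7.4.2 notes that subjects may have several insomnia episodes, and it pools four insomnia terms into one combined term. Insomnia also matters clinically: Protocol 4.3 names it as the main cause of TEAE discontinuations in the earlier adult ADHD study (11.2% at 4 mg/day and 29.7% at 8 mg/day).

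The ordering also contrasts with how the SAP treats incomplete AE dates in 6.1.11.3.1, where "A conservative approach will be used to handle the missing dates for AE onset date and end date". No reason is given for ranking missing attributes the other way.

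The two-category display raises a separate question: where does an event with no recorded causality go? This one does not depend on repeat records.

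**Working it through.** The plan states no figure to reproduce. The check applies the rankings as written, and then as proposed under the fix.

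**Step 1. One record in the row.** Outcome missing gives 'unknown'; relationship or severity missing gives 'not specified'. Nothing is recoded to recovered, not related or mild.

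**Step 2. A missing-class record plus one known record in the same row.** Displayed value = the higher-ranked of the two.

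| Attribute | Known value on the other record | Shown, SAP order | Shown, missing class just above most benign |
|---|---|---|---|
| Outcome | recovered | recovered | unknown |
| Outcome | recovered with sequelae | recovered with sequelae | recovered with sequelae |
| Outcome | recovering | recovering | recovering |
| Outcome | not recovered | not recovered | not recovered |
| Outcome | fatal | fatal | fatal |
| Relationship | not related | not related | not specified |
| Relationship | related | related | related |
| Severity | mild | mild | not specified |
| Severity | moderate | moderate | moderate |
| Severity | severe | severe | severe |

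The two orders differ only where the other record has the most benign value. Every worse known value is shown under both.

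**Step 3. Illustration of size for outcome (all inputs assumed).** Take 20 subjects in a row with an unknown-outcome record. Let *s* be the share who also have a known-outcome record in that row, and *q* the share of those whose known outcome is recovered.

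- SAP order: shown unknown = 20(1 − s); shown recovered = 20·s·q; shown at another known outcome = 20·s·(1 − q).
- Proposed order: shown unknown = 20(1 − s) + 20·s·q; shown recovered = 0; other known outcomes unchanged.

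| s | q | SAP: unknown | SAP: recovered | SAP: other known | Proposed: unknown |
|---|---|---|---|---|---|
| 0 | any | 20 | 0 | 0 | 20 |
| 0.1 | 0.5 | 18 | 1 | 1 | 19 |
| 0.1 | 1 | 18 | 2 | 0 | 20 |
| 0.3 | 0.5 | 14 | 3 | 3 | 17 |
| 0.3 | 1 | 14 | 6 | 0 | 20 |
| 0.5 | 0.5 | 10 | 5 | 5 | 15 |
| 0.5 | 1 | 10 | 10 | 0 | 20 |

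The masked share, s·q, simply restates the assumptions. The documents give neither *s* nor *q*, nor the number of unknown outcomes.

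**Step 4. The two relationship texts side by side.** The two-category display defines both categories by an investigator's judgement. A record without that judgement meets neither definition. The 'AE maximum relationship' text has a third class for it but does not say how that class enters the two-category table. The drug-related rows require a related event. As written, a missing causality therefore does not count there, even for a subject with one record.

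**The case against.** The strongest reply is that the rule neither invents nor recodes data. Missing values keep their own class, and the rule shows a known value in preference to a missing one, whether that known value is good or bad: unknown plus not recovered shows not recovered, and 'not specified' plus severe shows severe. All AEs are listed, the safety analyses are descriptive, and the incidences of AEs, SAEs and discontinuations due to AEs named in the primary objective do not change. The rule for incomplete dates decides whether an event counts as treatment-emergent; it is not a general principle for missing attributes. Elsewhere the SAP leaves missing scale items unimputed and does not class missing compliance as non-compliance.

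Most of this stands, and it limits the point to repeat-record subjects and secondary displays. It does not remove the masking in Step 2, and listings do not correct a summary table.

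A reader might infer more: that events left open when a subject drops out are generally reported as recovered, not related or mild. The documents do not support that.

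- Single-record subjects remain 'unknown' or 'not specified'.
- An event known to be open has its own code, 'not recovered/not resolved', which ranks above everything except fatal. Nothing says that sites should use 'unknown' instead.
- Loss to follow-up bears on outcome. Protocol 12.3 requires each AE to be evaluated for severity and causality, and nothing links missing values of those two to dropout.
- A reader might also infer that any other PT in the same SOC overrides an unknown. The SAP's wording on the level of the maximum can be read that way, but it does not settle whether a maximum is taken on SOC or combined-term rows.

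On the two-category display, the reply is that the later text plainly defines three classes, so a programmer would add a row. That may well happen for the table. It still leaves the drug-related rows without a rule.

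**Conclusion.** The point holds in limited form. For subjects with more than one record in the same row, ranking the missing class lowest lets the most benign known value hide a missing one. Where this ordering differs from the proposed one, it always gives the more favourable display. Single-record subjects and overall incidences are unaffected. The number of subjects concerned could be very small, and the documents do not allow an estimate. The illustration rests wholly on assumed shares, and its extension to SOC or combined-term rows depends on an ambiguous phrase.

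The mismatch between two categories and three classes is a separate gap in the text, independent of repeat records, and needs reconciling in any case. Taken together, this is a cheap improvement, not a threat to the primary safety objective.

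**What to change.** In SAP 7.4.2:

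1. Outcome order: recovered/resolved < unknown < recovered/resolved with sequelae < recovering/resolving < not recovered/not resolved < fatal.
2. Relationship order: not related < not specified < related.
3. Severity order: mild < not specified < moderate < severe.
4. State that missing causality counts as related in the two-category table and in the drug-related rows. Because that category is otherwise defined by investigator judgement, mark this as an analysis convention.
5. Footnote each affected table with the number of subjects who have any unknown or not-specified record.

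The missing class should go no higher than this. Ranking it above recovering, or above moderate, would hide known sequelae, recovering or moderate values and replace one masking rule with another.

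The cost is a few lines of SAP text and a small programming change, with no new data. The drug-related counts may rise slightly and the recovered counts may fall slightly.
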